5.2. Secondary objectives

The secondary objectives of this study are to assess the risk and compare it between E4/DRSP users and EE/LNG users (stratified by age, smoking, and BMI) for:

- All VTE, including thromboses of the renal, mesenteric, portal, cerebral and retinal veins⁷ (a sensitivity analysis will be done for the ICD-10 code I80.3),
- ATE, including acute myocardial infarction (AMI) (ICD-10 code I21.* 8) and cerebrovascular accidents (CVA) (ICD-10 code: I24.9, G45.*, I61.*, I63.1, I63.2, I63.3, I63.4, I63.5, I63.8, I63.9),

⁴ ClinicalTrials.gov identifier: NCT01009684

⁵ ClinicalTrials.gov identifier: NCT00335257

⁶ ClinicalTrials.gov identifier: NCT01650168

⁷ ICD-10 codes: I26.0, I26.9, I63.6, I67.6, I80.1, I80.2, I80.3, I80.8, I80.9, I81, I82.0, I82.2, I82.3, I82.8, I82.9, H34.8, K55.0 and N28.0

^{*} For all stars, it means including all codes within this category

Supporting document SOP PM01 - Doc PM3004.03

- Unintended pregnancy, and
- Neonatal malformations associated with foetal exposure to E4/DRSP and EE/LNG.
- Drug utilization pattern,
- Baseline risk profile for primary and secondary clinical outcomes—in particular for cardiovascular outcomes.

6. Research methods

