- Stillbirth (defined as foetal death with a gestational age ≥20 weeks)
- Neonatal death (defined as deaths occurring among live births during the first 28 completed days of life)
- Spontaneous/elective abortion (defined as a loss of pregnancy at a gestational age <20 weeks)
- Termination of pregnancy for foetal anomaly (TOPFA [where prenatal diagnosis was made of malformation in a live foetus and the pregnancy was then terminated])
- Preterm delivery (defined as delivery strictly before 37 completed weeks of gestation)
- Low birth weight (defined as a birth weight <2,500g)
- Small for gestational age infants

The list of variables in Table 1 are similar to the variables used in previous PASS conducted by ZEG-Berlin.

Supporting document SOP PM01 – Doc PM3004.03

Table 1: List of variables to be used in INAS-NEES

		Variable				
X - present; G - present in Germany only; U - present under 18 only; T - present, triggers additional follow up Participant Characteristics		p		Questionnaire		
		Baseline	Follow-up	Extra Follow-up		
	Screening	Did you take an oral contraceptive pill or any other hormonal contraceptive in the last 2 months?	Х			
		Before you were asked whether you want to take part in this study, you and your doctor decided on a new prescription for an oral contraceptive pill. Was the prevention of pregnancy the reason for this prescription?	G			
		Do you have (or have you ever had) a blood clot in a blood vessel of your legs (deep vein thrombosis, DVT), your lungs (pulmonary embolus, PE), or other organs?	G			
		Are you aware of having a disorder affecting your blood clotting – for instance, protein C deficiency, protein S deficiency, antithrombin-III deficiency, factor V Leiden, or antiphospholipid antibodies?	G			
		Do you need an operation or are you off your feet for a long time (e.g., hip/leg surgeries, neurological surgeries, trauma surgeries)?	G			
		Have you ever had a heart attack or a stroke?	G			
		Do you have (or have you ever had) angina pectoris (a condition that causes severe chest pain and may be a first sign of a heart attack) or transient ischaemic attack (TIA – temporary symptoms of stroke)?	G			
Participant Characteristics		Do you have severe diabetes with blood vessel damage?	G			
		Do you have very high blood pressure?	G			
		Do you have a severely increased blood lipids (cholesterol or triglycerides)?	G			
ant (Do you have a condition known as hyperhomocysteinaemia?	G			

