rticipa		Do you have (or have you ever had) a type of migraine called 'migraine with aura'?	G			
Pa		Do you have (or have you ever had) a tumour in the liver (benign or malignant)?	G			
		Do you have (or have you ever had) a serious liver disease and your liver function is still not normal?	G			
		Are your kidneys not working well (renal insufficiency)?	G			
		Do you have (or have you ever had) breast cancer or cancer of the genital organs, or is there a suspicion of such a cancer?	G			
		Do you have any unexplained bleeding from the vagina?	G			
		Are you allergic to estetrol or drospirenone, or any of the other ingredients (Lactose monohydrate, Sodium starch glycolate, Maize starch, Povidone K30, Magnesium stearate (E470b), Hypromellose (E464), Hydroxypropylcellulose (E463), Talc (E553b), Cottonseed oil (hydrogenated), Titanium dioxide (E171), Iron (III) oxide red (E172))?	G			
	Demography	Year of birth	Х			
		Height	Х	U		
		Weight	Х	Х		
		Education level	Х			

		Variable		O		
Category		X - present; G - present in Germany only; U - present under 18 only; T - present, triggers additional follow up		Questionnair	re	
Pai	articipant Characteristics		Baseline	Follow-up	Extra Follow-up	
	Gynaec. history	Age at first menstrual period	Х			
		Problems related to period	Х			
		Ever been pregnant before	Х			
		Pregnant in the last 3 months	Х			
		Number of live births	Х			
		Age at first delivery	Х			
	Regular	Taking regular medication	Х	Х	Х	
	Medication	Brand name of regular medication	Х	Х	Х	
Ris	sk Factors		Baseline	Follow-up	Extra Follow-u	
	Family History	Any DVT/PE in close relatives	Х		1 Ollow-u	
	ne como necos de la constitución	Close relatives who experienced DVT/PE	X			
		Any MI/Stroke related death in close relatives	Х			
		Close relatives who died as result of MI/Stroke	Х			
	Diseases	Participant's knowledge of their own risk-factor diseases/conditions	Х			
	Deep Vein	Date of being informed about DVT diagnosis	Х			
	Thrombosis	Was DVT treated by physician?	Х			
		Was DVT treated with blood-thinners?	Х			
	Pulmonary Embolism	Date of being informed about PE diagnosis	Х			
		Was PE treated by physician?	Х			
		Was PE treated with blood-thinners?	Х			
	Myocardial	Date of being informed about MI diagnosis	Х			
1	Infarction	Was MI treated by physician?	Х			
actors		Did ECG/laboratory confirm MI?	Х			
Fact	Stroke	Date of being informed about Stroke diagnosis	Х			
Risk		Was Stroke treated by physician?	Х			

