6.4. Data sources

At study entry (baseline), study participants will sign an ICF and complete a baseline questionnaire designed to capture data on potential confounding factors and potential effect modifiers. Study participants will record personal information such as their age, height, weight, educational level, personal medical history, family medical history of VTE and ATE, concomitant medication, history of hormonal contraceptive use, and smoking status (see Section 6.4.1).

Study participants will complete follow-up questionnaires at 6, 12, 18, and 24 months after entering the study. The follow-up questionnaires will capture information on HC use, the occurrence of specified AEs of interest, and unintended pregnancy (see Section 6.4.2). Data on potential confounding factors (e.g., BMI and smoking status) will also be recorded during the follow-up phase.

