6.4.1. Baseline survey

Eligible study participants who agree to participate will complete a baseline survey on which they will record demographic data (age, height, and weight), personal medical history (including gynaecological history and medication use), family history of relevant risk factors, previous hormonal contraceptive use, education level, and lifestyle data (e.g., smoking status). The questionnaire will be sent out after successful consenting to the patient via email. The patient can decide if they want to fill out the questionnaire at the HCP via smartphone or tablet or if they want to do it at home on their electronic device.

The baseline questionnaire can be completed at HCP's office or home via the electronic data capture (EDC) system or if EDC is not feasible, through Computer Assisted Telephone Interviews (CATI).

If the study participant does not answer the initial request to answer the baseline questionnaire, two reminders are sent 7 days apart. If these reminders are unsuccessful, 4 attempts will be made by telephone over 14 days. After these contact attempts the baseline questionnaire will be blocked and the patient is not eligible for the study.

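### Table 1 records only fatal MI or stroke in close relatives, although Section 6.4 promises family history of ATE, so non-fatal events in relatives have no variable

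*Protocol*

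**What the plan says.** Two sections of the protocol describe the baseline family history in general terms. Section 6.4 lists "family medical history of VTE and ATE" among the items each woman records. Section 6.4.1 speaks of "family history of relevant risk factors". Neither restricts the arterial part to deaths.

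Table 1 in Section 6.3.2, the list of study variables, has four family-history rows, all collected at baseline in every country:

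- VTE: a row on any DVT or PE in close relatives, then "Close relatives who experienced DVT/PE".
- ATE: "Any MI/Stroke related death in close relatives", then "Close relatives who died as result of MI/Stroke".

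Two parts of the plan would use the arterial information. Section 5.2 lists as a secondary objective the "Baseline risk profile for primary and secondary clinical outcomes", with emphasis on cardiovascular outcomes. The same section compares ATE between the cohorts, and the endpoint is not limited to fatal events. Section 6.7.1 proposes propensity-score weighting to correct covariate imbalance. Section 6.5 describes ATE as a secondary outcome for which a 2.5-fold risk is to be excluded.

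**The concern.** The narrative and the variable list do not match. For VTE the list covers what Section 6.4 promises. For ATE it covers only the fatal part. A woman whose father survived an MI at an early age answers no to both arterial rows, truthfully, and nothing else in Table 1 records the event. The MI and stroke rows elsewhere in the table concern the participant herself.

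This cannot be left to a later analysis plan, because no analysis can recover a question that was not asked. What is at stake is limited. The cardiovascular risk profile would show a family history of arterial death, not of arterial disease. If prescribers take such a history into account when choosing between the two products, the weights for the ATE comparison could balance only the recorded part of it.

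**Working it through.** **1. Text comparison.** The plan states no figure on this point, so there is none to reproduce.

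| | Promised in Section 6.4 | Collected in Table 1 |
|---|---|---|
| Family VTE | yes | any event, and which relatives |
| Family ATE | yes | deaths only, and which relatives died |

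Non-fatal MI or stroke in a relative is the one cell that is promised and not collected.

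**2. How much a death-only item captures.** Let f be the share of affected relatives who died of the event and k the number of affected relatives. Treating relatives as independent, the item finds a positive family history with probability 1 − (1 − f)^k. The documents do not give f, so a range is assumed.

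| f | k = 1 | k = 2 |
|---|---|---|
| 0.1 | 10% | 19% |
| 0.3 | 30% | 51% |
| 0.5 | 50% | 75% |
| 0.7 | 70% | 91% |

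More than half of positive histories are missed only if f is below 0.5 (k = 1) or below 1 − √0.5 ≈ 0.29 (k = 2).

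**3. Illustrative effect on the ATE hazard ratio.** All inputs are assumptions: any family ATE in p1 = 15 to 20% of one cohort and p0 = 10% of the other; relative risk RR = 2 to 3; death-item sensitivity s = 0.2 to 0.4 with specificity 1; cohorts of equal size.

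- Unadjusted bias factor: [1 + p1(RR − 1)] / [1 + p0(RR − 1)]. Smallest: 1.15/1.10 = 1.045. Largest: 1.40/1.20 = 1.167.
- Women with a positive death item all have the family history, so no confounding by it remains among them. Their pooled share is d = s(p1 + p0)/2.
- Among women with a negative item, the remaining prevalence is n = p(1 − s)/(1 − ps) in each cohort.
- After weighting over the whole cohort, the relative risk in each cohort is d·RR + (1 − d)[1 + n(RR − 1)], and the residual factor is the ratio of the two.

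Smallest residual (p1 = 0.15, RR = 2, s = 0.4): d = 0.05, n1 = 0.0957, n0 = 0.0625, giving 1.1410/1.1094 = 1.028.

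Largest residual (p1 = 0.20, RR = 3, s = 0.2): d = 0.03, n1 = 0.1667, n0 = 0.0816, giving 1.3833/1.2184 = 1.135.

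The residual factor is therefore about 1.03 to 1.14. If the imbalance ran the other way, the factor would be the reciprocal, 1/1.135 = 0.88 to 1/1.028 = 0.97.

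**4. A milder assumed imbalance.** With 25% against 20% and RR = 2, the unadjusted factor is 1.25/1.20 = 1.042. Balancing the death item alone leaves 1.038 (s = 0.1) down to 1.015 (s = 0.7).

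**The case against.** The strongest reply is that the gap is narrow and may close by itself. Annex 1 lists the baseline questionnaire as a stand-alone document still to be finalised, so its wording could turn out wider than Table 1. Section 6.3.2 says the variables resemble those of earlier studies by the same group, so the death-only rows may be kept for comparability. The protocol does not fix family ATE history as a propensity covariate, and the weighting text in Section 6.7.1 concerns VTE. All of this stands, and it keeps the point minor. It does not remove the mismatch, because Table 1 is the list the questionnaire should follow.

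Three stronger readings are tempting, and the documents do not support them.

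- *Most family history of ATE is recorded as absent.* The share of fatal events among relatives is not given, and step 2 shows that the answer turns on it. The item also records correctly that there was no death. Non-fatal history is unrecorded, and it becomes absent only if the item is used as a stand-in for any family ATE.
- *Family history of ATE cannot be described or balanced.* The fatal part can be.
- *A past TIA outside Germany cannot be told from a new one.* Follow-up in all countries asks about diagnoses made since the last contact, with dates and, for stroke, type and symptom duration. Reported ATE is then validated (Section 6.4.3) and adjudicated blind (Annex 3.2).

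A reader may also notice that "Do you have a severely increased blood lipids (cholesterol or triglycerides" and "Do you have (or have you ever had) angina pectoris" appear only in Germany-only screening rows. That does not show these conditions go uncollected elsewhere. The all-country rows on known risk-factor conditions, other severe disease and regular medication may capture them, and Table 1 does not list what the general condition row covers.

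**Conclusion.** The inconsistency is real and minor. Section 6.4 promises family history of ATE, Table 1 collects only its fatal part, and non-fatal MI or stroke in relatives has no variable. That finding rests on the text alone and needs no assumption beyond the questionnaire following Table 1.

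The consequence is partial description in the cardiovascular risk profile and partial balance in the secondary ATE comparison. The primary VTE analysis is untouched, since family DVT/PE is collected for any event. The residual factor of about 1.03 to 1.14 is an illustration of scale, not an estimate: the prevalences, the relative risk and the sensitivity are all assumed. Even at its upper end it is small beside a 2.5-fold margin.

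**What to change.** In Table 1, change the two death-only rows to *Any MI/stroke (fatal or not) in close relatives* and *Which relatives, and whether it was fatal*, in parallel with the DVT/PE rows. Carry the wording into the baseline questionnaire before it is finalised, and make the item available as a covariate for the ATE analysis. If the sponsor prefers to keep the death-only rows, Section 6.4 should at least say that only arterial deaths in relatives are recorded.

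The cost is two reworded rows and a small change from the wording of earlier studies. Because fatality is still recorded, the death-only variable can be rebuilt for comparison with them.

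Naming raised lipids and previous TIA or angina as baseline risk-factor items in all countries is optional, since existing rows may already capture them.

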6.4. Data sources

At study entry (baseline), study participants will sign an ICF and complete a baseline questionnaire designed to capture data on potential confounding factors and potential effect modifiers. Study participants will record personal information such as their age, height, weight, educational level, personal medical history, family medical history of VTE and ATE, concomitant medication, history of hormonal contraceptive use, and smoking status (see Section 6.4.1).

Study participants will complete follow-up questionnaires at 6, 12, 18, and 24 months after entering the study. The follow-up questionnaires will capture information on HC use, the occurrence of specified AEs of interest, and unintended pregnancy (see Section 6.4.2). Data on potential confounding factors (e.g., BMI and smoking status) will also be recorded during the follow-up phase.

6.4.1. Baseline survey

Eligible study participants who agree to participate will complete a baseline survey on which they will record demographic data (age, height, and weight), personal medical history (including gynaecological history and medication use), family history of relevant risk factors, previous hormonal contraceptive use, education level, and lifestyle data (e.g., smoking status). The questionnaire will be sent out after successful consenting to the patient via email. The patient can decide if they want to fill out the questionnaire at the HCP via smartphone or tablet or if they want to do it at home on their electronic device.

The baseline questionnaire can be completed at HCP's office or home via the electronic data capture (EDC) system or if EDC is not feasible, through Computer Assisted Telephone Interviews (CATI).

If the study participant does not answer the initial request to answer the baseline questionnaire, two reminders are sent 7 days apart. If these reminders are unsuccessful, 4 attempts will be made by telephone over 14 days. After these contact attempts the baseline questionnaire will be blocked and the patient is not eligible for the study.

6.4.2. Follow-up phase

Follow-up will be conducted via direct contact with the participants through EDC or, where EDC is not feasible, CATI. At each pre-defined follow-up time point (i.e., 6, 12, 18, and 24 months after study entry), study participants will be contacted and asked to complete a follow-up web-based questionnaire, accessible via a link sent by SMS or email. The follow-up questionnaire will be designed to capture data on contraceptive use, specific safety outcomes (e.g., VTE, ATE, MI, or stroke), weight, and pregnancy outcomes. If the patient does not complete the questionnaire on the initial contact attempt, two reminders are sent 7 days apart. If these reminders do not lead to success, 4 attempts will be made by telephone during the next 14 days, starting 7 days after the last reminder E-mail. After these contact attempts the follow-up questionnaire will be blocked and the patient will be set to lost to follow-up.

Supporting document SOP PM01 - Doc PM3004.03

In the case study participants report OC exposure during pregnancy, the women will be followed-up on the outcome of the pregnancy. To obtain the necessary information, an extra follow-up questionnaire will be provided to the respective study participants 3 months after their anticipated date of delivery. The prevalence estimates of major congenital malformation for COC users will be compared with the general population. The total prevalence of major congenital malformations, and live birth prevalence, will be calculated as per EUROCAT definitions.

6.4.3. Validation of self-reported events

If a health outcome of interest (VTE, ATE, or pregnancy) is reported by a study participant by positively answering the respective question in the study questionnaire, it is automatically flagged in the database, and the study participant is immediately asked for more details within the electronic data capture (EDC) system. Flagged follow-up questionnaires are then reviewed by the medical event validation team at ZEG Berlin. Following review, it may be necessary to re-contact the study participant and/or the treating HCP for validation of the information initially received from the study participant. For this purpose, the study participant gives permission to contact the treating physician who has diagnosed the outcome of interest (not necessarily the same as the recruiting HCP) in case the participant cannot provide any valid medical documentation. Necessary information that is unclear or missing will be cross-checked with the study participant and/or HCP for clarification. All additional information received by the medical event validation team is captured in the study database and forms part of the core study dataset.

A self-administered questionnaire used by study participants at short intervals is a sensitive tool that captures almost all serious clinical outcomes and was already used in similar studies [7]. From a methodological point of view, it captures a much higher proportion of these outcomes than methods relying only on the prescribing HCP who may not be involved in the diagnosis and treatment of these outcomes. However, there is a significant difference between the rates of patient-reported and medically confirmed events after validation, as laypersons often misclassify specific AEs, and therefore validation of the self-reported events is of utmost importance.

In this study, a medical confirmation will be sought for self-reported events considered as VTE or ATE captured in the study database. VTE and ATE cases will be classified by ZEG Berlin's medical event validation team according to the following predefined algorithm:

- Definite Event:

Diagnosis confirmed by diagnostic measures with high specificity (DVT: e.g., phlebography, duplex sonography, and magnetic resonance imaging; PE: e.g., pulmonary angiography, ventilation-perfusion scan, magnetic resonance imaging, transesophageal echocardiography, and spiral computed tomography (CT); cerebral magnetic resonance imaging (MRI) for cerebrovascular accidents, electrocardiography (ECG) with typical ST-segment elevation for acute myocardial infarction)) and written proof e.g., medical record.

- Probable Event:

Absence of confirmation by a diagnostic measure with high specificity for the diagnosis, but clinical diagnosis confirmed (verbally or in writing) by an HCP or, supported by diagnostic tests with low specificity (such as ultrasound doppler, plethysmography, D-dimer for VTE or typical ECG/blood gas tests for PE).

These cases are usually characterized by a subsequent specific therapy (such as fibrinolysis or long-term anticoagulant therapy). However, if the attending physician

Supporting document SOP PM01 - Doc PM3004.03

confirms that the diagnosis is correct, the event will be classified as a VTE, even if specific treatment was not given.

Definite and probable events will be classified as 'confirmed events'

Possible Event:

Study participant (self-reported) diagnosis of VTE or ATE without a medical confirmation of the event or, no diagnostic measures were performed that could have clarified the diagnosis however, the case history provided (e.g., symptoms, treatment) strongly suggests that this is indeed a VTE/ATE case.

- Potential Event:

Condition considered as VTE or ATE was reported by the study participant only and no further medical confirmation could be obtained, and the case history is not sufficiently clear to allow further clarification.

- Event disproven:

Diagnosis reported by the study participant is excluded by diagnostic procedures or a different medical condition is diagnosed by the attending HCP.

Possible, potential, and disproven events will be classified as a subgroup of 'not confirmed' events.

The classification of VTE and ATE into 'confirmed' and 'not confirmed' will be verified during the blinded adjudication procedure. At least three individual medical specialists (adjudicators) will review available information on the reported outcomes and classify the case as "confirmed" or "not confirmed". For this process, the adjudicator will be blinded to the brand names and composition of the treatments used by the reporting study participant. The adjudicators will perform the reviews independently of each other and without knowing the judgement of the other adjudicators or the investigators. Details of the procedure are given in *Annex 3.2*.

